15.0 Sample Size

We plan to enroll 31 patients, allowing for 10% ineligibility, to obtain 28 patients evaluable for primary end point, overall response rate.

12. Fanale, M.A., et al., *Brentuximab Vedotin Administered Concurrently with Multi-Agent Chemotherapy As Frontline Treatment of ALCL and Other CD30-Positive Mature T-Cell and NK-Cell Lymphomas*. ASH Annual Meeting Abstracts, 2012. **120**(21): p. 60-.
13. **ORAL PRESENTATIONS**. Hematological Oncology, 2013. **31**(S1): p. 96-150.

14. Krathon, M., et al., *Brentuximab Vedotin Demonstrates Significant Clinical Activity in Relapsed or Refractory Mycosis Fungoides with Variable CD30 Expression*. ASH Annual Meeting Abstracts, 2012. **120**(21): p. 797-.
15. Bodo, J., L. Durkin, and E.D. Hsi, *Quantitative in situ detection of phosphoproteins in fixed tissues using quantum dot technology*. J Histochem Cytochem, 2009. **57**(7): p. 701-8.
16. Agnelli, L., et al., *Identification of a 3-gene model as a powerful diagnostic tool for the recognition of ALK-negative anaplastic large-cell lymphoma*. Blood, 2012. **120**(6): p. 1274-81.
17. Gallamini, A., et al., *Peripheral T-cell lymphoma unspecified (PTCL-U): a new prognostic model from a retrospective multicentric clinical study*. Blood, 2004. **103**(7): p. 2474-9.

APPENDIX 1
ECOG PERFORMANCE STATUS CRITERIA

| ECOG Performance Status Scale | |
|--------------------------------------|---|
| Grade | Descriptions |
| 0 | Normal activity. Fully active, able to carry on all pre-disease performance without restriction. |
| 1 | Symptoms, but ambulatory. Restricted in physically strenuous activity, but ambulatory and able to carry out work of a light or sedentary nature (e.g., light housework, office work). |
| 2 | In bed < 50% of the time. Ambulatory and capable of all self-care, but unable to carry out any work activities. Up and about more than 50% of waking hours. |
| 3 | In bed > 50% of the time. Capable of only limited self-care, confined to bed or chair more than 50% of waking hours. |
| 4 | 100% bedridden. Completely disabled. Cannot carry on any self-care. Totally confined to bed or chair. |
| 5 | Dead. |

APPENDIX 2

IWC RESPONSE CRITERIA (adapted from [1])

| IWC+PET-Based Response Designations | Description |
|-------------------------------------|---|
| CR | CR by IWC with a completely negative PET CRu, PR, or SD by IWC with a completely negative PET and a negative BMB if positive prior to therapy PD by IWC with a completely negative PET and CT abnormalities (new lesion, increasing size of previous lesion) ≥ 1.5 cm (≥ 1.0 cm in the lungs) and negative BMB if positive prior to therapy |
| CRu | CRu by IWC with a completely negative PET but with an indeterminate BMB |
| PR | CR, CRu, or PR by IWC with a positive PET at the site of a previously involved node/nodal mass CR, CRu, PR, or SD by IWC with a positive PET outside the site of a previously involved node/nodal mass SD by IWC with a positive PET at the site of a previously involved node/nodal mass that regressed to < 1.5 cm if previously > 1.5 cm, or < 1 cm if previously 1.1-1.5 cm |
| SD | SD by IWC with a positive PET at the site of a previously involved node/nodal mass (i.e., residual mass) |
| PD | PD by IWC with a positive PET finding corresponding to the CT abnormality (new lesion, increasing size of previous lesion) PD by IWC with a negative PET and a CT abnormality (new lesion, increasing size of previous lesion) of < 1.5 cm (< 1.0 cm in the lungs) |

Abbreviations: IWC+PET, International Workshop Criteria plus positron emission tomography; CR, complete response; BMB, bone marrow biopsy; CT, computed tomography; CRu, unconfirmed complete response; PR, partial response; SD, stable disease; PD, progressive disease.

APPENDIX 3

International Prognostic Index (IPI)

| |
|--------------------------------|
| Age > 60 |
| Serum LDH above normal |
| Stage III-IV |
| ECOG PS ≥ 2 |
| >1 extranodal site involvement |

Each characteristic receive 1 point each and the total score ranges from 0-5

APPENDIX 4

Prognostic Index for PTCL (PIT) Score

| |
|-------------------------|
| Age > 60 |
| Serum LDH above normal |
| ECOG PS ≥ 2 |
| Bone marrow involvement |

Each characteristic receives 1 point each and the total score ranges from 0-4 [17]

APPENDIX 5

Summary of Protocol Changes

New Protocol Version #/Date: 5/13/2016
Previous Protocol Version #/Date: 3/25/2015

Rational for Changes: Most changes are formatting the protocol/consent. Additionally, we added missed tests that originally should have been included.

| Section #/Page # | Change | Rationale |
|--------------------------------------|---------------------------|--|
| Throughout Protocol | Corrected formatting | Cleaner versions |
| Study Table/ Page 40 & 43 | Added Echo | Missed from original protocol. Heart function should be checked |
| Study Table / Page 43 | Added LDH | Ordered separately from CMP |
| Treatment / Page 41 | Added section 11.1.7 | Specifies ability to continue after cycle 17 |
| Treatment / Page 40 | Added Vital Signs | Missed from original protocol |
| Access EMR / Page 47 | Removed Coordinator Names | Change to often to be listed in protocol. Specified in Data Management plan. |

New Protocol Version #/Date: 8/20/2016
Previous Protocol Version #/Date: 5/13/2016

| Section #/Page # | Change | Rationale |
|--|--|---|
| Throughout Protocol | Corrected formatting | Cleaner versions |
| Throughout Protocol | Defined Contraceptive period to 6 months | FDA guidance |
| Inclusion Criteria / Pg. 4 &15 | Added defined ECOG of 3 to 4.1.4 | Updated for patients for active disease otherwise ok. |
| Inclusion Criteria / Pg. 4 &15 | Defined 4.1.9 | Clarification |
| Exclusion Criteria / Pg. 4 & 16 | Defined 4.2.2 XRT and Steroid Use | Clarification |
| Treatment Plan / | Treatment | Clarification |

| | | |
|--|---|--|
| Pg. 17 | discontinuation defined | |
| Treatment Plan / Pg. 18 | No window added to Cycle 1 day 1 | Clarification |
| Duration of Follow Up / Pg. 20 | Defined serum chemistry Panel and added specifics to CT's to adverse event follow up. | Clarification |
| Tissue Procurement / Pg. 34 | Defined Instructions for shipping and retaining samples | Clarification |
| Screening / Pg. 36 | Added PIT score, CT scan instructions, BM Biopsy defined. | PIT scoring I specific to disease. Scans and Biopsy are just Clarifications. |
| Cycles & Study Table / Pg. Multiple | Outlined expectation for LDH, Uric Acid and Phosphorus | All 3 are ordered separately from CMP and required at specific time points |
| Cycles & Study Table / Pg. Multiple | Defined Adverse event collection | Clarification |
| Study Table / Pg. 39 | Added PIT, Split AE's/Conmeds, Added Uric Acid and Phosphorus | Clarification |
| Appendix | Added Appendix 3 & 4 | Scoring Systems |

New Protocol Version #/Date: 11/19/2016

Previous Protocol Version #/Date: 8/20/2016

Rational for Changes: All Administrative updates

| Section #/Page # | Change | Rationale |
|----------------------------|--|--|
| Title Page / Page 2 | Added NCT # | Mandated by Scientific Review Committee |
| SAE's / Page 26 | Removal of [name] and addition of [name] | [name] has left the program and [name] has taken over her duties. |

New Protocol Version #/Date: 7/20/2017
Previous Protocol Version #/Date: 11/19/2016

Rational for Changes: Administrative updates to protocol and adding risk of pneumonitis

| Section #/Page # | Change | Rationale |
|---------------------------------------|---|---|
| Title Page / Page 2 | Adding external sites (Hacksack and University of Michigan) | Sites preparing to open study, need added to protocol |
| 11.1.6 / Page 26 | Clarifying CT scans to be done at Cycles 4 and 10 (5 day window so scans should be done between days 15 and 20) | Previous verbiage (day 15-20) was unclear and inconsistent |
| 11.4 / Page 38 | Clarifying window for CT scans performed at Cycles 4 and 10 | The protocol defined 5 day window was not clear in previous version |
| 13.1 & 13.2.4 / Page 41-42 | Updating EMR information for University Hospitals and Overture language for data collection | Previous version was outdated |
| 9.3.1 / Page 31 | Adding risk of Pneumonitis | This is important information in the current IB |

New Protocol Version #/Date: 9/27/2018
Previous Protocol Version #/Date: 7/20/2017

| Section #/Page # | Change | Rationale |
|--|---|---|
| Schema / Pages 3&4 4.1 & 4.2./ Page 14&15 | Removing transformed mycosis fungoides as an approved indication for enrollment in this study | Recent FDA approval of the study drug for this indication. Patients with transformed mycosis fungoides may no longer enroll on this study |
| Schema / Page 3 | Adding splenomegaly as indicator of | Updated for patients with splenomegaly |

| | | |
|---|---|--|
| | measurable disease | |
| Schema / Page 5 4.2/ Page 15 | Reducing treatment washout time from 4 to 2 weeks before start of study drug | Updated to allow patients with rapid disease progression to enroll without delaying treatment |
| 6.2 / Page 17 | The threshold for dose recalculation based on change in body weight is being changed from 5% to 10% | This change was made to be consistent with the pharmacy instructions distributed by Seattle Genetics |
| 7.0 / Pages 20&21 | Adding information on when the study drug may be held or modified | Previously the protocol did not provide guidance on when the study drug could/should be held |
| 8.3 / Page 25 | Updating CCF SAE reporting contact information | Previous contact information was outdated. |
| 10.3 / Pages 34 | Updating information on shipping slides | Previous information was outdated and further detailed instructions are stated to be located in the Manual of Operating Procedures |

New Protocol Version #/Date: 2/6/2020

Previous Protocol Version #/Date: 9/27/2018

| Section/Page | Change | Rationale |
|------------------------|--|--|
| Pages 1 & 2 | Updated Karmanos PI and other administrative information | Updated to the most current information |
| Section 4.1 | Corrected numbering for some inclusion criteria | Fixing incorrect numbering of items |
| Section 7.0 | Adding information on when to hold BV | More detailed was added on how to appropriately hold BV for BV-related toxicities |
| Pages 34-39 | Details were added in the schedule of assessments | Height is only required at screening. Clarification that screening and C1D1 is allowed on the same day. Certain EOT procedures are not required for patients with disease progression. |

New Protocol Version #/Date: 8/21/2020
Previous Protocol Version #/Date: 2/6/2020

| Section/Page | Change | Rationale |
|---------------------------------|--|--|
| Section 6.7.2 & 11.3 | Allowing virtual visits for long-term follow up visits | Increasing flexibility to more reliably capture long-term follow up data |

New Protocol Version #/Date: 7/6/21
Previous Protocol Version #/Date: 8/21/2020

| Section/Page | Change | Rationale |
|---|---|--|
| Title Page / Page 1/Section 16 | Updating Karmanos PI to [name] | Change in site PI |
| Title Page / Page 2 | Removing [name] and [name]., [name] Adding [name] | Personnel updates |
| Section 10.2 | Processing for T-qPCR Assay for CD30 updated from [name] to the RT-PLMI facility | The RT-PLMI facility will now complete sample processing |
| Section 10.3 | Change Cleveland Clinic Biorepository shipping title and ATTN to [name] | Title correction and pathologist replacement |
| Schema Page 3, Section 2.3, Section 10.0 | References to Nuance FX multispectral Imaging camera deleted or changed to Asperio image analysis | To align with current PLMI processes. |
| Section 8.3 | SAE contact info updated | To reflect personnel updates at CCF. |
| Section 6.7.2, 11.3, study calendar | Clarifying that if a virtual visit is completed in follow up, assessments not completed will not be considered a protocol deviation. Patients that start new treatment enter survival follow up. | For patient convenience. |
| 13.1 | Overture changed to Advarra | To be consistent with current EDC used. |

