11.2 End of Study Treatment Visit

End of study visit will be conducted within 30-45 days of last cycle of therapy

- Physical Examination
- Vital signs
- Height and weight
- Concomitant medication documentation, including over the counter medication and supplements
- CBC with differential
- Serum chemistry panel as mentioned above
- LDH
- Pregnancy test for females of childbearing potential
- ECOG performance status (not required if patient has disease progression)
- Adverse event evaluation

- Diagnostic CT of neck, chest, abdomen, pelvis with IV and oral contrast and PET scan to be done between 30-45 days after the last cycle of therapy. Neck CT can be omitted at the discretion of the investigator if there was no involvement at baseline. If unable to obtain both CT and PET scan due to insurance restrictions, either CT or PET are acceptable, but PET scan is preferred
 - For patients coming off treatment due to disease progression, scans are only required, if the last scan within 60 days did not show disease progression. If the patient had a scan within the last 60 days that document progression, no further scans are needed.
- BM biopsy to be repeated between 30-45 days after the last cycle of therapy if it was positive prior to start of the study drug.
 - BM biopsy may be omitted for patients who are coming off treatment due to disease progression.

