12.2 Definitions

12.2.1 Primary Endpoint

12.2.1.1 Overall Response Rate

The primary objective is to evaluate overall response rate (ORR). Overall response rate will be estimated by the total number of patients who achieve a CR and PR divided by the total number of evaluable patients. Response will be assessed using CT scans according to the revised Cheson criteria [1].

- CR is defined as complete resolution of all clinically detectable disease and disease related symptoms that were present prior to therapy
- PR is defined as at least 50% decrease in sum of the product of the diameters (SPD) of up to six of the largest dominant nodes or nodal masses

Patients should have completed at least 1 cycle of treatment to be evaluable for ORR.

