12.2.2.2 Progression Free Survival

Progression-free survival (PFS) is defined as the time from enrollment into the study to disease progression or death due to any cause. The distribution of PFS will be estimated using the Kaplan-Meier method. Disease progression may be defined as the date of documentation of a new lesion or enlargement of a previous lesion, or the date of the scheduled clinic visit immediately after radiologic assessment has been completed. For a patient who is alive without progression at the end of study follow-up, observation of PFS is censored on the date of last contact.

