12.2.2.4 Duration of Response

Duration of response (DOR) is defined as the time from first documentation of objective tumor response (CR or PR) to the time to tumor progression or death due

to any cause.

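### Appendix 2 scores some PET-negative CT progression as complete response, section 12.2.2.2 describes the same finding as progression, and nothing says which rule prevails

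*Combined protocol and SAP*

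**What the plan says.** Appendix 2 is a response table adapted from the same reference that section 12 cites for response. Its CR row ends with "PD by IWC with a completely negative PET and CT abnormalities (new lesion, increasing size of previous lesion) ≥ 1.5 cm", subject to the further conditions "≥ 1.0 cm in the lungs) and negative BMB if positive prior to therapy". The PD row has two lines. One covers a positive PET matching the CT abnormality. The other is "PD by IWC with a negative PET and a CT abnormality (new lesion, increasing size of previous lesion) of < 1.5 cm", with a 1.0 cm limit for the lungs.

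Section 12.2.2.2 defines PFS as "the time from enrollment into the study to disease progression or death due to any cause" and adds: "Disease progression may be defined as the date of documentation of a new lesion or enlargement of a previous lesion". It also allows the date of the clinic visit after imaging. It sets no PET condition and no size limit, and does not refer to Appendix 2. Section 12.2.2.4 defines DOR as "the time from first documentation of objective tumor response (CR or PR) to the time to tumor progression or death". Section 14.0 sends the reader to section 12.2 for endpoint definitions.

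Imaging on treatment is CT only, at cycles 4 and 10 (section 11.1.6). CT plus PET comes 30 to 45 days after the last cycle (section 11.2), where either scan alone is accepted if insurance does not cover both. For patients stopping because of progression, section 11.2 says: "If the patient had a scan within the last 60 days that document progression, no further scans are needed".

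**The concern.** Two stated rules classify the same finding in opposite ways. A new or growing lesion of at least 1.5 cm that is PET-negative is a complete response under the table and progression under the PFS definition. An analyst who follows both would put the patient in the numerators of ORR and CR, record a PFS event, and compute a DOR that starts and ends on the same date.

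The classification can also depend on logistics. With CT alone, the finding is progression under section 12.2.2.2. With CT plus a completely negative PET, Appendix 2 makes it a CR. Whether PET is done can depend on insurance cover or on the scan waiver in section 11.2. Under section 12.3 the treating investigator at each site reviews response, and no central review is described. Sites could therefore apply different rules and each be following the protocol.

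The primary endpoint is exposed because the decision rule is a count out of 28, so one patient can decide it.

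**Working it through.** **Step 1: compare the two rules for a new or growing CT lesion.**

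| Finding | Appendix 2 | Section 12.2.2.2 |
|---|---|---|
| At least 1.5 cm, PET positive at the lesion | PD | progression |
| Under 1.5 cm, PET negative | PD | progression |
| At least 1.5 cm, PET completely negative, marrow condition met | CR | progression |
| Any size, PET not done | no row (every row needs a PET result) | progression |

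(In the lungs, read 1.0 cm for 1.5 cm.) The third line is the contradiction. The fourth shows why the result can depend on whether PET was done.

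**Step 2: follow a third-line patient at the end-of-treatment visit.** Under Appendix 2 the patient adds one to ORR and one to CR, each worth 1/28 = 3.6 percentage points. Under section 12.2.2.2 the same assessment is a PFS event. If the response is first documented there, DOR = progression date minus response date = 0.

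**Step 3: reproduce the plan's figures.** Inputs from section 14.0: n = 28, promising if 8 or more respond, unacceptable rate 15%, promising rate 35%. With X ~ Binomial(28, p):

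- P(X ≥ 8 | 0.15) = 0.0486, against the stated 5% level.
- P(X ≥ 8 | 0.35) = 0.8179, against the stated 82% power.

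Both reproduce. The conflict changes none of these inputs.

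**Step 4: sensitivity to one patient.** 7/28 = 25.0% (exact 95% CI 10.7% to 44.9%) misses the rule. 8/28 = 28.6% (13.2% to 48.7%) meets it. The chance of exactly 7 responses is 6.7% at a true ORR of 15% and 9.0% at 35%.

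**Step 5: an assumed reclassification rate.** The documents give no rate. Let m be the share of non-responders scored CR through the Appendix 2 line. The counted response probability is p' = p + (1 − p)m. At p = 0.15 there are 28 × 0.85 = 23.8 expected non-responders.

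| m (assumed) | p' | Expected reclassified (23.8 × m) | P(X ≥ 8) |
|---|---|---|---|
| 0 | 0.1500 | 0 | 4.9% |
| 1% | 0.1585 | 0.24 | 6.4% |
| 2% | 0.1670 | 0.48 | 8.2% |
| 3% | 0.1755 | 0.71 | 10.4% |
| 5% | 0.1925 | 1.19 | 15.5% |

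The upper end of the range corresponds to about one such patient per trial.

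**The case against.** **Section 12.2.2.2 may only be a dating rule.** It says how progression may be defined as a date, and offers an alternative date. On that reading progression is established elsewhere, Appendix 2 governs, and nobody is counted twice. This reading is available, but the text does not state it. The sentence stands under the heading for definitions, is section 12's only description of progression, and lies in the section that 14.0 names for endpoint definitions.

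**The body text leans on CT.** Sections 12.1 and 12.2.1.1 assess response by CT. Section 12.2.2.1 lets a PET-negative residual mass count as CR but does not mention new or growing lesions. The CR count therefore arises only if Appendix 2 is applied. That stands as a qualification. Against it, the Schema refers to CT/PET, section 12.1 uses PET at end of treatment, and Appendix 2 is the protocol's only response table, from the same cited source.

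**Few patients would be affected.** PET is scheduled only at baseline and end of treatment, the PET must be completely negative, and the marrow condition must be met. This stands, and it limits the size of the problem.

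**Stronger readings that a reader might infer.** One is that DOR becomes negative. That needs an earlier CT progression followed by a PET that section 11.2 does not require; the text leads directly only to zero. Another is that the false-positive rate becomes 11.5% or 23.5%, which are P(X ≥ 7) and P(X ≥ 6) at 15%. These are correct binomial tails, but they assume one or two reclassified patients in every trial, which nothing in the documents supports. A third is that the CR-row line is plainly an error, since a PET-negative lesion of 1.4 cm is PD and one of 3 cm is CR. The matching thresholds in the CR and PD rows may be deliberate, and the cited source is not available to settle it.

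**Conclusion.** The contradiction is in the text and should be resolved. It is a conflict between two stated rules, not a missing detail. Following both can give one patient a CR, a PFS event and a DOR of zero.

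Its effect is unknown and probably small. Under the assumed 1% to 5% reclassification of non-responders, the chance of declaring the regimen promising at a true ORR of 15% is 6.4% to 15.5% instead of 4.9%. This treats the section 12.2.2.2 reading as the reference and assumes that Appendix 2 is applied when responses are counted. Sample size and stated power are unaffected.

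The documents do not show which progression rule is right. Progression is also a reason for stopping treatment (sections 3.2 and 6.1), so that choice belongs to the sponsor.

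**What to change.** Reconcile Appendix 2, section 12.2.2.2 and section 12.2.2.4 so that one progression definition, chosen by the sponsor, applies to ORR, CR, PFS and DOR. Cite Appendix 2 by name in section 12.2 if it is operative. Assign every PET/CT combination to exactly one category, including CT without PET.

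- If the CR-row line is removed, the PD row must be amended as well. It now covers PET-negative lesions only below 1.5 cm (1.0 cm in the lungs), so deletion alone would leave the larger ones with no category.
- If the line is kept, sections 12.2.2.2 and 12.2.2.4 must carry the same PET exception.

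In either case, state in sections 12.2.1.1 and 12.2.2.1 that a response counts only if first documented before progression under that definition.

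The cost is wording only, with no new data. ORR and the CR rate may come out slightly lower.

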14.0 STATISTICAL CONSIDERATIONS

Please refer section 12.2 for endpoint definitions. The primary objective is to evaluate overall response rate. For this patient population, response of 15% or less is unacceptable and 35% or more is promising. Twenty-eight evaluable patients will be accrued; if 8 or more patients respond, then the regimen will be considered promising. The significance level of this one-sided test is 5%, and the power is 82%.

Other end points analyzed are CR, PFS, OS, DOR, and TTF. ORR and CR will be estimated using exact 95% confidence intervals. PFS and OS will be estimated using the Kaplan-Meier method. DOR and TTF will be estimated using standard descriptive statistics such as median and range, or mean and standard deviation.

McNemar's test will be used to compare incidence of CD30 positivity via IHC with multi- spectral imaging and RT-PCR to see if different methods result in different findings.

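### Appendix 2 scores CT-stable disease with PET uptake outside prior nodal sites as PR, which conflicts with the response and progression definitions in section 12.2; a site using the appendix could count a non-responder towards ORR

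*Combined protocol and SAP*

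**What the plan says.** Appendix 2, adapted from reference [1], combines a CT-based category with PET. One line of its PR row reads "CR, CRu, PR, or SD by IWC with a positive PET outside the site of a previously involved node/nodal mass". Its SD row reads "SD by IWC with a positive PET at the site of a previously involved node/nodal mass (i.e., residual mass". Both lines of the PD row start from PD on CT.

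Section 12.2.1.1 assesses response on CT under the revised Cheson criteria, also citing [1], and states: "PR is defined as at least 50% decrease in sum of the product of the diameters (SPD", taken over up to six of the largest dominant nodes or nodal masses. ORR counts CR and PR over evaluable patients.

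Section 12.2.2.2 states: "Disease progression may be defined as the date of documentation of a new lesion or enlargement of a previous lesion". It names no imaging modality. As an alternative date it allows the scheduled clinic visit just after the radiologic assessment.

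Section 14.0 refers to section 12.2 for endpoint definitions and then gives the decision rule: "For this patient population, response of 15% or less is unacceptable and 35% or more is promising", and "Twenty-eight evaluable patients will be accrued; if 8 or more patients respond, then the regimen will be considered promising". The Schema says response is assessed with CT/PET. Section 12.3 assigns response review to the treating investigator at each site.

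**The concern.** Take two patients with the same stable CT at end of treatment. One has PET uptake only at the original node, and Appendix 2 calls this SD. The other has uptake somewhere else, and Appendix 2 calls this PR. If that second focus is a new lesion, the patient with the worse finding gets the better category. No PD line catches the case, because CT does not show progression.

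If the appendix is used, that patient enters the ORR numerator with no tumour shrinkage. The same finding fits the section 12.2.2.2 description of progression. The patient could then be a responder for ORR and DOR and a PFS event on one date, with a response duration of zero. The primary decision turns on 8 responders among 28, so a single misclassified patient matters.

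**Working it through.** **1. The same patient under each text.** CT stable, no 50% SPD fall, new FDG-avid site seen on PET only.

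| Text | Classification |
|---|---|
| Appendix 2, PR row | PR |
| Appendix 2, SD row | Does not apply (uptake is not at the old node or nodal mass) |
| Appendix 2, PD row | Does not apply (CT is not PD) |
| Section 12.2.1.1 | Not PR, so a non-responder |
| Section 12.2.2.2 | Progression, if the focus counts as a new lesion |

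The three texts give three different answers.

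**2. When it can arise.** PET is scheduled at baseline and end of treatment (section 11.4). The assessments at cycles 4 and 10 use CT only (section 12.1). Section 11.2 schedules CT and PET at end of treatment but accepts either alone under insurance restrictions. It asks for no further scan if one within the last 60 days documented progression. The exposed group is therefore patients who have both scans at end of treatment, stable CT, and uptake outside prior nodal sites.

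**3. The plan's own figures.** Inputs from section 14.0: n = 28, success at 8 or more responders, null rate 15%, promising rate 35%. Exact binomial:
- P(X ≥ 8 | 28, 0.15) = 0.0486, within the stated 5%.
- P(X ≥ 8 | 28, 0.35) = 0.818, matching the stated 82%.

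The design calculation is sound.

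**4. Sensitivity to misclassified patients, true rate 15%.**
- One of the 28 is certain to be a false responder, so 7 are needed from the other 27: P(X ≥ 7 | 27, 0.15) = 0.0986.
- One false responder is added on top of 28 patients who each respond with probability 15%, so the true-responder threshold falls to 7: P(X ≥ 7 | 28, 0.15) = 0.115.
- Two of the 28 are certain to be false responders: P(X ≥ 6 | 26, 0.15) = 0.185.

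**5. Sensitivity to a misclassification share.** Let q be the share of true non-responders scored PR by this line. The scored rate is 0.15 + 0.85q. The documents give no value for q, so the range is an assumption.

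| q | Scored rate | P(X ≥ 8 of 28) |
|---|---|---|
| 0 (section 12.2.1.1 applied) | 0.150 | 0.049 |
| 2% | 0.167 | 0.082 |
| 5% | 0.1925 | 0.155 |
| 10% | 0.235 | 0.329 |

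**The case against.** The strongest reply is that Appendix 2 does not feed the primary endpoint. Section 14.0 sends the reader to section 12.2, where PR needs a 50% SPD fall on CT, and no text in sections 12 or 14 invokes the appendix. This largely stands. A reader might infer that every CT-stable patient with uptake elsewhere adds a false responder to the 8-of-28 decision. The documents do not support that, because under section 12.2.1.1 the number is zero. What remains is ambiguity in use: the shared reference [1], the Schema's CT/PET wording, and reading by each site's treating investigator. The appendix is also the only table of response categories in the document.

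A second reply is that uptake outside a previously involved node need not be spread. Section 12.1 records extranodal masses at baseline, and section 4.1.9 admits patients on splenomegaly or marrow involvement. This stands too. A reader might infer that the row always rewards new disease, but it also covers extranodal disease present from the start. In that case the conflict is with the 50% SPD requirement only, not with section 12.2.2.2. The wording of section 12.2.2.2 is itself permissive.

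Third, the exposed group is narrow, as step 2 of the working shows, and a new lesion that makes CT progressive with matching PET falls in the PD row. This limits frequency but does not remove the contradiction.

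Finally, reference [1] is not available here, so whether the row is a slip or the source's wording cannot be settled. The need to reconcile it with section 12.2 does not depend on that.

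**Conclusion.** The contradiction is real and should be resolved before response is finally classified. Appendix 2 assigns PR to CT-stable patients whom section 12.2.1.1 treats as non-responders and, where the focus is a new lesion, whom section 12.2.2.2 describes as progressing.

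The effect on ORR is conditional. It is nil if section 12.2.1.1 is applied throughout and arises only where a site scores from the appendix at the end-of-treatment CT/PET. Given one such patient, the false-positive rate at a true 15% roughly doubles, from 4.9% to between 9.9% and 11.5%. These are sensitivities: the documents give no frequency, and the single-patient figures take the misclassification as having occurred. The stated significance level and power are correct for the rule as written.

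**What to change.** 1. State in both section 12.2.1.1 and Appendix 2 that the section 12.2 definitions govern ORR wherever the two differ. This also settles the neighbouring PR line, which scores SD as PR on regression of a PET-positive node below a size limit without asking for a 50% SPD fall.
2. Amend the Appendix 2 PR row so that CT-stable disease with PET uptake outside prior nodal sites does not count as PR for ORR:
   - A new FDG-avid site judged to be lymphoma is classified consistently with section 12.2.2.2 and is neither CR nor PR.
   - CT-stable disease with uptake at an extranodal site already involved at baseline goes in the SD row.

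Simply striking SD from the PR line would not be enough. A CT-stable patient with uptake only at a known extranodal site would then fit no row: CR needs a negative PET, SD needs uptake at the node or nodal mass, and PD needs PD on CT.

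The cost is a few lines of text and no new data. The reported ORR may be slightly lower, and Appendix 2 would depart from its cited source at this row, which the appendix should say.
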